9.4.10 Pharmacokinetic Analyses

Pharmacokinetic concentrations for OKZ in plasma will be summarized descriptively by scheduled collection time and dose regimen. Time to steady state will be graphically evaluated for the OKZ trough data collected over the study period.

For the PK subpopulation, plasma OKZ PK parameters will be summarized descriptively by dose regimen and study day. Accumulation of OKZ over time will be evaluated descriptively, and if appropriate with an exploratory inferential analysis. Pharmacokinetic relationships will be explored graphically and with linear or nonlinear modeling approaches, as appropriate. Data collected in this study may be combined with data from other OKZ studies in support of population PK analyses.

Concentration data for the ADA/PK matched subjects will only be analyzed and presented as part of the PK summaries if the subject has a positive ADA response during the Treatment Period. These data will be included the population PK analyses, as appropriate.

The related endpoints are described in in Section 4.4. Further details for the PK analysis will be provided in the SAP.

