The references cited above for ACR20 and DAS28 response rates are assumed to reflect approximately 10% of subjects discontinuing randomized treatment prior to Week 12. In this study, subjects who discontinue prior to Week 12 will be classified as nonresponders for the primary endpoint of ACR20 at Week 12 as well as for the secondary endpoint of DAS28 (CRP) <3.2 at Week 12.

The primary endpoint as well as the secondary endpoints that are binary in nature will be analyzed using a 2x2 chi-squared test for equality of proportions for each OKZ treatment group compared with placebo.

Based on the treatment effect assumptions and the methodology for estimating sample size via simulation to ensure sufficient disjunctive power as described above, a sample size of 420 subjects randomized in a 1:1:1 ratio (140 subjects per treatment group) will yield 100% disjunctive power for testing the primary hypothesis (ACR20 at Week 12) and 98% disjunctive power for the evaluation of the secondary endpoint of DAS28 (CRP) <3.2 rate at Week 12.

Analysis Populations

- Intent-to-treat (ITT) population: The ITT population will include all randomized subjects. Subjects will be analyzed according to the treatment group to which they were randomized. The ITT population will be the primary analysis population.
- Modified Intent-to-treat (mITT) population: The mITT population will include all randomized subjects who receive at least 1 dose of study treatment. Subjects will be analyzed according to the treatment group to which they were randomized. The mITT population, if sufficiently different from the ITT population (>5% of ITT subjects excluded from mITT across all treatment groups), will be used for supportive analyses of the primary and secondary efficacy endpoints.
- Per Protocol (PP) population: The PP population will include all ITT subjects who do not have any major protocol violations. Subjects will be analyzed according to the treatment group to which they were randomized. Major protocol violations and the inclusion of subjects in the PP population will be finalized prior to study unblinding. The PP population will be used for supportive analyses of the primary and secondary efficacy endpoints.

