Each of the OKZ treatment groups (64 mg q2w and 64 mg q4w) will be compared with placebo for each of the primary, secondary, and other endpoints. The overall Type I error rate will be controlled for testing hypotheses of the primary and secondary endpoints at the overall 1-sided $\alpha = 0.025$. The α -control strategy will be based on using the Bonferroni adjustment for the tests related to each of the 2 OKZ dose regimens versus placebo (i.e., using the 1-sided $\alpha = 0.0125$ for each dose regimen). A gate-keeping strategy will be used for tests associated with the primary and secondary endpoints for each OKZ dose regimen independently with the same order of testing as the secondary endpoints are defined above. In other words, each OKZ dose regimen will be tested at 1-sided $\alpha = 0.0125$ for a given endpoint if null hypotheses are rejected at 1-sided $\alpha = 0.0125$ for this dosing regimen for all previous endpoints based on the established order. Conversely, the testing will stop for a given OKZ dose regimen at the endpoint for which the null hypothesis is accepted at 1-sided $\alpha = 0.0125$.

Pharmacokinetic Analysis

In the subjects with periodically collected OKZ concentrations, OKZ results will be summarized descriptively by scheduled collection time and dose regimen. Time to steady state will be graphically evaluated for the OKZ trough data collected over the study period.

For the PK subpopulation, PK parameters for OKZ will be summarized descriptively by dose regimen. Accumulation over time will be evaluated descriptively, and, if appropriate, with an exploratory inferential analysis. Pharmacokinetic/PD relationships will be explored graphically and with linear or non-linear modeling approaches, as appropriate. Data collected in this study may be combined with data from other OKZ studies in support of population PK analyses. Olokizumab concentration for the ADA/PK matched subjects will only be analyzed and presented as part of the PK summaries if the subject has a positive ADA response during the Treatment Period. These data will be included the population PK analyses, as appropriate.

Safety Analysis

Major components for the safety analysis will include:

- AEs will be solicited at every study visit, recorded, and coded according to the most recent version of

the Medical Dictionary for Regulatory Activities (MedDRA).

- SAEs
- Vital signs and physical examination findings
- Laboratory parameters

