7.2 Pharmacokinetics

Blood samples (approximately 2 mL/sample) for determination of OKZ concentrations in plasma will be collected from all subjects. Olokizumab in plasma will be assessed as follows:

- All subjects: Blood samples for measurement of OKZ concentrations will be collected at each time a blood sample is taken for the determination of ADAs (ADA/PK matched subjects), with the exception of the final Safety Follow-Up Visit (Visit SFU-3). However, OKZ concentrations will only be analyzed and reported for subjects who have a confirmed positive ADA response in any of the postdose samples.
- PK subpopulation: In approximately one third (33%) of subjects (approximately 140 consenting subjects), additional blood samples will be collected periodically

throughout the study for analysis of OKZ in plasma to be included in a population PK assessment.

- Sample-rich PK subpopulation: In at least 42 of the 140 consenting subjects in the PK subpopulation, additional ICF will be consented and serial blood samples will be collected following the first dose of study treatment (Week 0) and over a 4-week period at steady state (Weeks 20 through 24) to reach appropriate number of the enrolled subjects for further analysis of PK parameters. Olokizumab PK parameters will be determined by using noncompartmental analysis in subjects randomized to OKZ following single (Week 0) and multiple dose (Week 20) administration, as appropriate.
 - The IWRS will be constructed to select consenting subjects to be included in the PK subpopulation in a blinded fashion based on the group to which they are randomized.
 - Subjects in the sample-rich PK subpopulation should use the same SC injection site (either abdomen or thigh) to administer the study treatment at Visit 2 and Visit 13 unless otherwise medically indicated.

All PK samples will be collected at the sampling times shown in Table 5. Blood samples will be taken either by direct venipuncture or an indwelling cannula inserted in a forearm vein. Details on sample processing, handling, shipment, and storage are provided in a separate Laboratory Manual. Tubes and preprinted labels will be provided by the central laboratory to the study sites.

The following information will be captured for blood PK sample collection in each subject's eCRF:

- Patient number and initials
- Date and time of study treatment administration for the last 2 visits preceding the PK sample collection
- Date and time of the blood PK sample collection

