- For subjects in the sample-rich PK subpopulation only, Visit 13 (Week 20) should be scheduled to fall within 14 ± 2 days after Visit 12 (Week 18) and 28 ± 3 days after Visit 11 (Week 16), and Visit 14 (Week 22) and Visit 15/EoT (Week 24) should be scheduled to fall within 14 ± 1 days and 28 ± 1 days, respectively, relative to study treatment administration at Visit 13 (Week 20).
- For subjects rolling over into the OLE study, the PK sample must be collected prior to the first dose of study treatment in the OLE study.
- For subjects who discontinue study treatment prior to the final scheduled dose, Visits SFU-2 and SFU-3 will occur +8 and +22 weeks, respectively, after the last dose of study treatment.
- At Visit SFU-3, blood samples will be collected for ADA analysis only; PK samples will not be collected.

Plasma will be analyzed, using appropriate bioanalytical methods, by R-Pharm or R-Pharm's designee for determination of OKZ concentrations. Full details of the analytical method used will be described in a separate bioanalytical report. Only samples from the subgroup of subjects receiving OKZ who consented to have samples taken for population PK analysis and/or serial PK analysis are initially scheduled to be analyzed. Samples from subjects receiving OKZ and not part of the planned PK analyses will only be analyzed in the case of a confirmed positive ADA response (see Section 7.3). If formation of ADAs is observed in any sample for a given subject, all OKZ PK samples will be analyzed for this subject. Samples from placebo subjects will not be analyzed.

Samples must be within the known stability of OKZ at the time of receipt by the bioanalytical laboratory to be analyzed.

Details on sample processing, handling, shipment, and storage are provided in a separate Laboratory Manual.

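### PK concentration summaries can mix an ADA-blind one-third sample with only the ADA-positive remainder, over-representing ADA-positive subjects by 3/(1+2p)

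*Combined protocol and SAP*

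**What the plan says.** Section 7.2 sets up two routes to an assayed concentration.

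- **PK subpopulation.** "In approximately one third (33%) of subjects (approximately 140 consenting subjects), additional blood samples will be collected periodically". These subjects are chosen through the IWRS by treatment group, with no reference to ADA status, and their samples are scheduled for assay from the start.
- **Everyone else on olokizumab.** Samples from subjects "not part of the planned PK analyses will only be analyzed in the case of a confirmed positive ADA response". Once a subject is positive, all of that subject's PK samples are assayed. Placebo samples are not assayed.

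Section 9.4.10 then gives the descriptive analysis: "Pharmacokinetic concentrations for OKZ in plasma will be summarized descriptively by scheduled collection time and dose regimen". Time to steady state is read from a plot of troughs. For subjects whose PK samples accompany ADA samples, the data "will only be analyzed and presented as part of the PK summaries if the subject has a positive ADA response" within the Treatment Period, and they also go into population PK where appropriate. PK parameters are summarized for the PK subpopulation.

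The synopsis (Pharmacokinetic Analysis) repeats the rule: "Olokizumab concentration for the ADA/PK matched subjects will only be analyzed and presented as part of the PK summaries". Its opening sentence, however, ties the by-visit, by-regimen summary to subjects sampled periodically. Section 9.4.10 does not carry that limit. Section 9.3 has one PK population, with no split by route of entry or ADA status. Further PK detail is left to the SAP.

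**The concern.** Whether a subject outside the PK subpopulation enters the concentration summaries depends on a post-baseline outcome, ADA positivity. Section 4.5 lists the impact of ADAs on olokizumab PK as something the study will evaluate, so the plan itself treats this variable as possibly related to the quantity being summarized. If both routes feed one table or plot, the result describes a mix enriched for ADA-positive subjects and not the treated population. Characterizing population PK and individual exposure is a secondary objective (Section 3.2), so what is at stake is how well the reported concentrations represent those treated. Efficacy conclusions and type I error are not involved.

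**Working it through.** **1. The plan's own figures.** The synopsis and Section 9.1 plan "420 subjects randomized in a 1:1:1 ratio (140 subjects per treatment group", so 280 subjects receive olokizumab. The PK subpopulation is 140/420 = 33.3%, as stated. Section 7.2 expects 13 to 14 sample-rich subjects per olokizumab group after the first dose and 11 to 12 at steady state, with 15% discontinuation. The check is 42/3 = 14, 14 × 0.85 = 11.9 and 13 × 0.85 = 11.05. These agree and support even selection across the three groups. The sampling fraction within olokizumab groups is therefore f = 1/3 (about 93 of 280), leaving about 187 outside.

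**2. Over-representation.** ADA-positive subjects are assayed with fraction 1 and ADA-negative subjects with fraction f. With true ADA incidence p:

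- pooled ADA-positive share s = p/[p + (1-p)f] = 3p/(1+2p)
- over-representation s/p = 3/(1+2p)

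In counts at p = 10%, there are 28 positive and 252 negative subjects. All 28 positives and 252/3 = 84 negatives are assayed. The pool is 112 and 28/112 = 25%, against a true 10%.

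**3. Bias of the mean.** Let r be the ADA-positive to ADA-negative ratio of mean concentration. Relative bias = [(1-s) + s·r]/[(1-p) + p·r] - 1. At p = 10% and r = 0.5 this is (0.75 + 0.125)/(0.90 + 0.05) - 1 = 0.875/0.95 - 1 = -7.9%.

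The protocol gives neither p nor r. Both are assumptions, shown over a range:

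| p | share s | s/p | r=0.25 | r=0.5 | r=0.75 | r=1 | r=1.25 |
|---|---|---|---|---|---|---|---|
| 1% | 2.9% | 2.94 | -1.5% | -1.0% | -0.5% | 0 | +0.5% |
| 5% | 13.6% | 2.73 | -6.7% | -4.4% | -2.2% | 0 | +2.1% |
| 10% | 25.0% | 2.50 | -12.2% | -7.9% | -3.8% | 0 | +3.7% |
| 20% | 42.9% | 2.14 | -20.2% | -12.7% | -6.0% | 0 | +5.4% |

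**4. Sensitivity to f.** If half of olokizumab subjects were in the PK subpopulation (f = 0.5), the factor 1/[p + (1-p)f] would be 1.90, 1.82 and 1.67 at p = 5%, 10% and 20%.

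**5. Visits.** In Table 5 the subjects outside the PK subpopulation have PK samples at Weeks 0, 4, 8, 12, 20, 24 and 30 (7 samples, matching the table's total). The PK subpopulation also has Weeks 1, 2, 14, 16 and 22 (12 in all without the serial samples, again matching). The enriched mix can therefore appear at Weeks 4, 8, 12, 20, 24 and 30, while Weeks 1, 2, 14, 16 and 22 come from the PK subpopulation alone. Week 0 is predose. With p = 10%, a constant r = 0.5 and a flat true profile, the plotted mean would rise by 0.95/0.875 - 1 = 8.6% from Week 12 to Week 16 and fall by 7.9% from Week 16 to Week 20, with no change in exposure.

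**6. After the fix.** The PK subpopulation alone has an expected ADA-positive share of p. Weighting its ADA-negative subjects by 3 gives 28/(28 + 84 × 3) = 28/280 = 10%.

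**The case against.** The strongest reply is that pooling is an inference. The synopsis opening can be read as already confining the main summary to the PK subpopulation, since periodic sampling is how the synopsis and Section 4.4 describe that group. A separate display of ADA-triggered subjects would also count as part of the PK summaries, and the SAP could separate the groups. This stands in part: the documents permit pooling and do not plainly order it. It does not remove the point. Section 9.4.10 drops the limit, both sections then add the ADA-triggered subjects, and nothing calls for a stratum or weights.

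Other parts of the reply stand in full:

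- A reader might infer that concentrations will be biased low. That requires r below 1, which no section states. At r = 1 there is no bias, and above 1 the bias is upward.
- A reader might quote a three-fold excess. Three is the limit as p approaches zero, where the bias also vanishes (between -1.5% and +0.5% at p = 1% over the ratios shown).
- Cmax, AUC, CL/F and accumulation are limited to the PK subpopulation and are not affected.
- Population PK need not be biased if ADA status is modelled, and ADA-triggered data enter it only where appropriate.
- A reader might infer a distorted comparison of q2w with q4w. Section 9.4.10 plans description by regimen, not a test between regimens.

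**Conclusion.** The point holds as a gap in Section 9.4.10 and the synopsis. As worded, concentration summaries and trough plots can combine two groups with sampling fractions of 1 for ADA-positive and about 1/3 for ADA-negative subjects. The over-representation follows from the sampling rule, given pooling and even selection across groups, and needs no assumption about the effect of ADA. It is 2.7, 2.5 and 2.1 times at assumed incidences of 5%, 10% and 20%. Any bias in the mean is conditional on ADA altering concentration: at 10% incidence, about -12%, -8%, 0 and +4% for assumed ratios of 0.25, 0.5, 1 and 1.25. The change of mix between visits is a second consequence, under the same condition, for the visual reading of steady state. The documents do not support a firm claim that exposure will be understated. The correction is worth making because the present rule can yield a descriptive summary that does not represent the treated subjects, and it is cheap to remove.

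**What to change.** In Section 9.4.10, restore the limit in the synopsis opening: base the descriptive concentration, trough and time-to-steady-state summaries on the PK subpopulation only. Name this as the group of about 140 in Section 7.2, because Section 9.3 uses the same label for subjects with a calculable PK parameter, a condition the synopsis attaches to the sample-rich group. Show ADA-triggered subjects from outside it in a separate table by ADA status. If the two groups are pooled anywhere, weight by the inverse of the sampling fraction. State in the population PK plan that ADA status is modelled when ADA-triggered data are used. Amend the ADA sentence in the synopsis to match.

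In the same edit, align the assay trigger: Sections 4.4 and 7.2 refer to a positive result in any postdose sample, while Section 9.4.10 refers to the Treatment Period.

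The cost is wording and one extra table, with no new samples, assays or subjects.

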9.4.11 Pharmacokinetic/Pharmacodynamic Correlations

The PK/PD relationship and immunogenicity of OKZ will be determined as described in the endpoints by Section 4.5. Analyses may include statistical comparisons and/or population PK/PD analyses. Further details for evaluation of PK/PD and PK/safety correlations will be provided in the SAP or a separate population PK/PD analysis plan.

9.4.12 Immunogenicity

Immunogenicity results including overall ADA results (Screening, confirmatory, and titers, as appropriate), neutralizing ADA results, and the time course of antibodies (defined as the time to first observation of a positive ADA response) will be listed. The number and percentage of subjects testing positive for ADAs or neutralizing antibodies will be summarized by dose treatment group over time. If applicable, the time course of antibodies may be summarized by treatment group using appropriate descriptive statistics.

9.4.13 Pharmacogenetics

The exploratory PG studies are designed to investigate the association between genetic factors (genotypes) and clinical assessments (phenotypes) which are collected during the clinical trial. Without prior evidence of a strong association, a number of possible associations are evaluated with exploratory analyses. A range of statistical tests (chi-square tests, ANCOVAs, linear and logistic regression) are used for the analyses. Additional data, from subsequent clinical trials, are often needed to confirm associations. Alternatively, if the numbers of subjects enrolled in the study are too small to complete proper statistical analyses, these data may be combined, as appropriate, with those from other studies to enlarge the data set for analysis.

9.4.14 Biomarkers

Soluble marker panel studies investigate differences in the level of expression of proteins or peptides between individuals in a given biofluid. The goal of such studies is to allow the identification of potential protein or peptide biomarkers of drug action or disease, and to better understand the associated underlying molecular mechanisms. By applying statistical analysis methods (e.g., principal component analysis) between subject groups, distinct study time points, or between study groups from other clinical trials, it may be possible to identify patterns which are associated with disease state or response to drug treatment. However, the exact type of data analysis method will depend on the type of data obtained in the study and thus the analysis of this data will be data driven.

9.4.15 Safety Analyses

Analysis of safety endpoints (see Section 4.7) will be done based on the safety population. Subjects in the safety population will be analyzed according to the treatment they actually received. Additionally to the primary safety analysis, the incidence of AEs will be analyzed separately for subjects administered additional DMARDs as rescue medication during the period of treatment without rescue medication and with rescue medication.

Major components for the safety analysis will include:

- AEs will be solicited at every study visit, recorded, and coded according to the most recent version of the MedDRA.
- SAEs.
- Vital signs and physical examination findings.
- Laboratory parameters.
- ECG and other specialized tests findings.

All safety assessments will be summarized in a descriptive manner. Further details will be provided in the SAP.

9.4.15.1 Adverse Events

All AEs will be analyzed in terms of descriptive statistics and qualitative analysis. Adverse events will be listed for each subject and summarized by SOC and PT according to the most recent version of the MedDRA. In addition, summaries of AEs by severity (evaluated using the CTCAE version 4.0) and relationship to study treatment will be presented. All safety and tolerability data recorded during the study will be listed and summarized by treatment group, and over time, as appropriate. Additionally to primary safety analysis, the incidence of AEs

will be analyzed separately for subjects administered additional DMARD as rescue medication during the period of treatment without rescue medication and with rescue medication.

Treatment-emergent AEs are defined as AEs that first occurred or worsened in severity after the first administration of the study treatment. Adverse event summaries will include incidence of TEAEs, SAEs including deaths, AEs that led to study treatment discontinuation, and AEs by maximum severity and relationship to study treatment. All summaries will be presented by MedDRA SOC and PT for each treatment group.

Safety/tolerability and AE data will be presented in individual listings.

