For subjects who receive rescue medication, periodic safety evaluations for toxicity resulting from sulfasalazine and/or hydroxychloroquine should be undertaken as per the drug label and local guidelines.

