The ACR20 response rate at Week 12 for the placebo group is estimated to be 25% in this study population (Genovese et al, 2008; Keystone et al, 2004; Weinblatt et al, 2003). The OKZ ACR20 response rates for 64 mg q4w and q2w treatment groups at Week 12 are expected to be at least 50% and 55% respectively, resulting in an expected difference in ACR20 response rates of 25 and 30 percentage points between respective OKZ treatment groups and placebo.

The DAS28 low disease activity (based on DAS28 [CRP] <3.2) response rate at Week 12 is estimated to be 10% in the placebo group (van der Heijde et al, 2006) and 22% and 30% in 64 mg q4w and q2w OKZ treatment groups respectively, resulting in an expected difference of 12 and 20 percentage points between respective OKZ treatment groups and placebo.

The references cited above for ACR20 and DAS28 response rates are assumed to reflect approximately 10% of subjects discontinuing randomized treatment prior to Week 12. In this study, subjects who discontinue prior to Week 12 will be classified as nonresponders for the primary endpoint of ACR20 at Week 12 as well as for the secondary endpoint of DAS28 (CRP) <3.2 at Week 12.

The primary endpoint as well as the secondary endpoints that are binary in nature will be analyzed using a 2×2 chi-squared test for equality of proportions for each OKZ treatment group compared with placebo.

Based on the treatment effect assumptions and the methodology for estimating sample size via simulation to ensure sufficient disjunctive power as described above, a sample size of 420 subjects randomized in a 1:1:1 ratio (140 subjects per treatment group) will yield 100% disjunctive power for testing the primary hypothesis (ACR20 at Week 12) and 98% disjunctive power for the evaluation of the secondary endpoint of DAS28 (CRP) <3.2 rate at Week 12.

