9.4.6 Multiple Hypothesis Testing

Each of the OKZ treatment groups (64 mg q2w and q4w) will be compared with placebo for each of the primary, secondary, and other endpoints. The overall Type I error rate will be controlled for testing hypotheses of the primary and secondary endpoints at the overall 1-sided $\alpha = 0.025$. The α -control strategy will be based on using the Bonferroni adjustment for the tests related to each of the 2 OKZ dose regimens versus placebo (i.e., using the 1-sided $\alpha = 0.0125$ for each dose). A gate-keeping strategy will be used for tests associated with the primary and secondary endpoints for each OKZ dose regimen independently with the same order of testing as the secondary endpoints are defined above. In other words, each OKZ dose regimen will be tested at 1-sided $\alpha = 0.0125$ for a given endpoint if null hypotheses are rejected at 1-sided $\alpha = 0.0125$ for this dosing regimen for all previous endpoints based on the established order. Conversely, the testing will stop for a given OKZ dose regimen at the endpoint for which the null hypothesis is accepted at 1-sided $\alpha = 0.0125$.

The above multiplicity control procedure will be applied to the primary analysis of the primary and secondary efficacy endpoints based on the ITT population, and will not be applied to sensitivity analyses of these endpoints.

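### The by-arm safety tables pool time before and after Week 14 rescue, and no rescue-free comparison of the randomized arms is pre-specified

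*Combined protocol and SAP*

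**What the plan says.** The main safety presentation is by arm over the whole study: "All safety and tolerability data recorded during the study will be listed and summarized by treatment group, and over time, as appropriate" (Section 9.4.15.1). The same section opens the treatment-emergent window at the first dose and gives it no cut at Week 14 or at the start of rescue. Section 9.4.15 uses the safety population by treatment received, keeps everything descriptive, and leaves further detail to the SAP.

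Under Section 6.13.3, subjects in any arm who have not improved by 20% in both joint counts at Week 14 receive sulfasalazine and/or hydroxychloroquine on top of their assigned treatment and stay on it for the rest of the study. For them, "periodic safety evaluations for toxicity resulting from sulfasalazine and/or hydroxychloroquine should be undertaken as per the drug label and local guidelines".

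The plan describes a rescue split in two ways:

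- Sections 9.4.15 and 9.4.15.1, and the synopsis: "the incidence of AEs will be analyzed separately for subjects administered additional DMARDs as rescue medication during the period of treatment without rescue medication" and during the period with it, so a before-and-after split inside rescued subjects.
- Section 9.3 (Safety population): rescued subjects set against subjects who never received rescue.

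For efficacy, Section 9.4.9.2 pre-specifies a sensitivity analysis for rescue (binary endpoints, Weeks 16 to 24). Safety has no between-arm counterpart.

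**The concern.** Placebo is the only reference for olokizumab harm. After Week 14 the arms differ in a second way, because rescue follows nonresponse and nonresponse is expected to be more common on placebo. Events caused by the rescue drugs, or found through evaluations done because of them, enter the by-arm tables at a rate that differs by arm.

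The protocol supplies the route. A laboratory abnormality judged clinically significant is recorded as an adverse event (Section 7.6.6). Hepatotoxicity, cytopenias and hypersensitivity are events of special interest (Section 7.6.3). Liver and blood-count thresholds lead to holding or stopping study treatment (Sections 6.11.1 and 6.11.2), so extra detection could also affect the table of events leading to discontinuation. Attribution will not separate the sources: Section 7.6.5 asks about relatedness to procedure, disease, study treatment and delivery system, and does not list rescue medication.

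At stake is whether the trial can describe olokizumab's harm over background methotrexate separately from harm due to rescue drugs.

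**Working it through.** **1. Plan's own figure.** The documents give no adverse-event rate, rescue rate or safety power. The only computed figure that uses these response rates is disjunctive power in Section 9.1, with "a sample size of 420 subjects randomized in a 1:1:1 ratio (140 subjects per treatment group") and one-sided alpha 0.0125 per regimen. Simulating the Bonferroni and gatekeeping scheme with a shared placebo arm (40,000 runs, several endpoint correlations) gives 99.9-100.0% for ACR20 and 98.4-98.5% for DAS28, against the stated 100% and 98%. The response rates are therefore read here as the plan uses them.

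**2. Rescue rates.** Section 9.1: "The ACR20 response rate at Week 12 for the placebo group is estimated to be 25% in this study population"; the q4w and q2w rates "are expected to be at least 50% and 55% respectively". ACR20 response requires the same 20% improvement in both joint counts and more, so ACR20 nonresponse is an approximate upper bound on rescue:

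- placebo 1 - 0.25 = 75%, 140 x 0.75 = 105 subjects
- q4w 1 - 0.50 = 50%, 70 subjects
- q2w 1 - 0.55 = 45%, 63 subjects

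Per arm, placebo's rate is 0.75/0.50 = 1.5 and 0.75/0.45 = 1.67 times the olokizumab rates. By count, placebo holds 105/238 = 44% of rescued subjects and the two olokizumab arms hold 133. The proxy is Week 12 rather than Week 14, and it counts the roughly 10% who discontinue as nonresponders, so actual rescue is probably lower.

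**3. Time affected.** Weeks 14 to 24 are 10/24 = 42% of the treatment period. The share of treatment time under rescue is up to 0.75 x 10/24 = 31.2% on placebo, 20.8% on q4w and 18.8% on q2w, a gap of 10.4 and 12.5 points.

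**4. Shift in the risk difference.** Let r be the excess event risk caused or detected because of rescue, equal in all arms. The documents give no value; 5%, 10% and 20% are assumed. The olokizumab-minus-placebo difference falls by (placebo rescue rate - olokizumab rescue rate) x r:

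| r | q4w (0.25 x r) | q2w (0.30 x r) |
|---|---|---|
| 5% | 1.25 points | 1.5 points |
| 10% | 2.5 points | 3.0 points |
| 20% | 5.0 points | 6.0 points |

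If only half of ACR20 nonresponders meet the joint-count rule in each arm, every entry halves. These are maxima only if the same fraction of ACR20 nonresponders is rescued in each arm. For a common outcome the shift is smaller, since some rescued subjects would have had an event anyway: with assumed true risks of 50% and 60% and r = 10%, the 10-point difference becomes 8.25 (q4w) and 8.05 (q2w).

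**5. On the rate scale.** If rescue's excess hazard equals olokizumab's own, the 24-week rate difference shrinks by 10/24 x 0.25 = 10.4% (q4w) and 10/24 x 0.30 = 12.5% (q2w). Erasing it would take a rescue hazard 9.6 or 8.0 times olokizumab's excess.

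**6. Direction.** If rescue is k times as toxic on olokizumab as on placebo, the shift is r x (k x olokizumab rescue rate - placebo rescue rate). It is zero at k = 1.5 (q4w) or 1.67 (q2w) and reverses above that.

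**7. Planned splits.** The before-and-after split uses only rescued subjects. The rescued-versus-not split sorts subjects by Week 14 response. Both condition on a post-randomization outcome that treatment affects, so neither compares the randomized arms free of rescue.

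**The case against.** The strongest reply is that one rescue rule applies to all arms, so the whole-study table is a valid randomized treatment-policy contrast, reported descriptively, and wanting another is a choice of estimand. That stands, and is why the table should be kept. It does not supply the other quantity, olokizumab's harm over methotrexate alone, for which nothing is specified. Summaries over time where appropriate, and detail deferred to the SAP, commit to no particular table.

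Several stronger readings are tempting and are not supported:

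- **Rescue falls mostly on placebo.** Not by count: 44% at planning rates. Only the per-arm rate is higher.
- **The difference is certainly biased toward zero.** That needs rescue toxicity to be similar across arms, which the documents do not address.
- **Rescued subjects certainly get extra tests.** Section 6.13.3 refers to labels and local guidelines. All arms already have hematology and chemistry at Weeks 16, 20, 24, 30 and 44.
- **Treatment and monitoring are identical before Week 14.** Retesting after abnormal results (Sections 6.11.1 and 7.6.3.4) and methotrexate adjustment (Section 6.1, Appendix 4) can differ by arm earlier. The early window is free of rescue, not of all outcome-driven monitoring.
- **Weeks 0 to 14 should become the main comparison.** That would drop 42% of treatment time, against the aim of at least 24 weeks of safety information (Section 2.3), and would miss late-onset harms.
- **Laboratory rates should use scheduled visits only, with rescue-related tests flagged.** That would discard mandated retests, and no field identifying such evaluations is described.

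**Conclusion.** The point holds in a limited form. The by-arm safety tables mix time before and after rescue. At planning rates rescue is proportionally more frequent on placebo (up to 75%, against 50% and 45%), and no comparison of the randomized arms before rescue is pre-specified. The whole-study contrast remains valid for treatment policy but is confounded by rescue as a measure of olokizumab's own harm.

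Attenuation is the expected direction, conditional on rescue being no more than about 1.5 to 1.67 times as toxic on olokizumab as on placebo. The size is illustrative only: it rests on ACR20 nonresponse as the proxy for rescue, a common rescued fraction of nonresponders across arms, and an assumed r of 5% to 20%. A reader might infer that a real safety signal will be hidden; the documents give no rescue toxicity rate from which to conclude that. The case for acting is that the plan cannot currently show whether rescue matters.

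**What to change.** In Sections 9.4.15 and 9.4.15.1 and the SAP:

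- Keep the whole-study by-arm tables and label them as including rescue.
- Beside them, pre-specify by-arm summaries of treatment-emergent events, serious events, events of special interest, events leading to discontinuation and laboratory abnormalities from first dose to the Week 14 visit, before any rescue dose. Apply the same cut to every subject whatever their response.
- Reconcile the rescue split in Section 9.3 with the one in Sections 9.4.15 and 9.4.15.1.

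The cost is wording and one extra set of tables from data already collected. The early-window tables will hold fewer events, and late-onset harms must still be read from the whole-study tables. Nothing changes in rescue or patient care.
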